#### 9.4 Analysis of Vital Signs

Vital sign variables include sitting systolic blood pressure, sitting diastolic blood pressure, pulse, body temperature, and weight. The criteria for potentially clinically significant vital sign findings are presented in Appendix C.

A treatment-emergent value is defined as a value with a date that is on or after the first dose of study drug, and no more than 30 days after the last dose of study drug.

The change from baseline mean, standard error, and 95% confidence interval will be presented for the mean change from baseline within each treatment group and difference between treatment groups using ANOVA model.

Vital sign variables will be evaluated based on potentially clinically significant (PCS) criteria (Appendix C). For each vital sign PCS criterion, the number and percentage of subjects who have a vital sign value meeting the criteria will be summarized. Listings will be provided to summarize subject-level vital sign data for subjects meeting PCS criteria.

## 9.5 Safety Subgroup Analyses

No planned safety subgroup analyses.

## 9.6 Other Safety Analyses

ECG is collected at screening visit, Week 2, Week 4, Week 8, and Week 12. ECG findings will be summarized by treatment group for each parameter and visit.

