6.2 Toxicity Management

The management of specific AEs and laboratory parameters is described in Table 4 and in the Operations Manual.

The toxicity management of the AEs including AESI consists of safety monitoring (review of AEs on an ongoing basis, and periodical/ad hoc review of safety issues by a safety data monitoring committee), interruption of study drug dosing with appropriate clinical management if applicable, and discontinuation of the subjects from study drug. The management of specific AEs and laboratory parameters is described below.

For subjects who discontinue study drug but continue study participation and are on standard of care therapies, these toxicity management requirements do not apply (including alerts from the central lab) and any intolerability to standard of care therapies should be managed by the prescribing physician.

Serious Infections: Subjects should be closely monitored for the development of signs and symptoms of infection during and after treatment with study drug. Study drug should be interrupted if a subject develops a serious infection or an opportunistic infection. A subject who develops a new infection during treatment with study drug should undergo prompt diagnostic testing appropriate for an immunocompromised subject. As appropriate, antimicrobial therapy should be initiated, and the subject should be closely monitored. Study drug may be restarted once the infection has been successfully treated. Subjects who develop active TB or experience hepatitis B reactivation must be discontinued from study drug. To further monitor subjects for serious infections, subjects will complete at-home weekly temperature monitoring. If above 100.5 degrees Fahrenheit (38 degrees Celsius), subject should inform their study doctor to assess the need for further evaluation.

Canada only: Investigators should be advised to follow local public health guidelines in order to prevent subjects enrolled in these trials from acquiring TB.

Serious Gastrointestinal Events: Subjects presenting with the onset of signs or symptoms of a serious gastrointestinal event should be evaluated promptly for early identification of gastrointestinal perforation. If the diagnosis of gastrointestinal perforation is confirmed, the subject must be discontinued from study drug.

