Cardiovascular Events (MACE): Subjects presenting with potential cardiovascular events should be carefully monitored. These events will be reviewed and adjudicated by the independent CAC.

Malignancy: Subjects who develop malignancy other than NMSC or carcinoma in situ of the cervix must be discontinued from study drug. Information including histopathological results should be queried for the confirmation of the diagnosis.

ECG Abnormality: Subjects must be discontinued from study drug for an ECG change considered clinically significant and with reasonable possibility of relationship to study drug OR a confirmed absolute QTcF value > 500 msec.

Management of Select Laboratory Abnormalities: For any given laboratory abnormality, the Investigator should assess the subject, apply the standard of care for medical evaluation and treatment following any local guidelines. Specific toxicity management guidelines for abnormal laboratory values

are described in Table 4 and may require an appropriate supplemental eCRF be completed. All abnormal laboratory tests that are considered clinically significant by the Investigator will be followed to a satisfactory resolution. If a repeat test is required per Table 4, the repeat testing must occur as soon as possible.

Table 4.	Specific 1	Foxicity	Management	Guidelines for	Abnormal	Laboratory	Values
	opeenie	· o/licity	in an agement	Garacinico ior	/ 10/10/11/10/1	Laboratory	- and c

Laboratory Parameter	Toxicity Management Guideline
Hemoglobin	• If hemoglobin < 8 g/dL interrupt study drug dosing and confirm by repeat testing with a new sample.
	 If hemoglobin decreases ≥ 3.0 g/dL from baseline without an alternative etiology, interrupt study drug dosing and confirm by repeat testing with new sample.
	• If hemoglobin decreases ≥ 3.0 g/dL from baseline and an alternative etiology is known, the subject may remain on study drug at the investigator's discretion.
	• If confirmed, continue to withhold study drug until hemoglobin value returns to normal reference range or its baseline value.
Absolute neutrophil count (ANC)	 If confirmed < 1000 cells/µL by repeat testing with new sample, interrupt study drug dosing until ANC value returns to normal reference range or its baseline value.
	 Discontinue study drug if confirmed < 500 cells/µL by repeat testing with new sample.

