#### Criteria for Potentially Clinically Significant Vital Sign Values Table C-2.

Vital Sign	Category	Criteria for Potential Clinically Significant Vital Signs
Systolic blood pressure	Low	Value $\leq$ 90 mmHg and/or decrease $\geq$ 20 mmHg from Baseline
	High	Value $\geq 160 \text{ mmHg}$ and/or increase $\geq 20 \text{ mmHg}$ from Baseline
Diastolic blood pressure	Low	Value $\leq$ 50 mmHg and/or decrease $\geq$ 10 mmHg from Baseline
	High	Value $\geq 100 \text{ mmHg}$ and/or increase $\geq 10 \text{ mmHg}$ from Baseline
Pulse	Low	Value $\leq$ 50 bpm and/or decrease $\geq$ 15 bpm from Baseline
	High	Value $\geq$ 120 bpm and/or increase $\geq$ 15 bpm from Baseline
Weight	High	>7% increase from baseline
	Low	> 7% decrease from baseline

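### The SAP has no subject-level count of QTcF or body temperature outliers, so measured values past the protocol's own figures can go unreported when no adverse event is recorded

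*SAP*

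**What the plan says.** **ECG.** Protocol 6.2 requires study drug to be stopped for a drug-related, clinically significant ECG change "OR a confirmed absolute QTcF value > 500 msec". ECGs are scheduled at Screening and Weeks 2, 4, 8 and 12. The SAP's analysis is one sentence in section 9.6: "ECG findings will be summarized by treatment group for each parameter and visit". SAP 10.0 adds nothing further, and Appendix C has no ECG criterion.

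**Body temperature.** SAP 9.4 states: "Vital sign variables include sitting systolic blood pressure, sitting diastolic blood pressure, pulse, body temperature, and weight". The same section says these variables will be assessed against the Appendix C PCS criteria, with counts, percentages and subject listings. Appendix C places the vital sign criteria in Table C-2, titled "Criteria for Potentially Clinically Significant Vital Sign Values". That table has rows for systolic pressure, diastolic pressure, pulse and weight only.

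**Home temperature log.** Protocol 6.2 explains its purpose: "To further monitor subjects for serious infections, subjects will complete at-home weekly temperature monitoring". It then gives a prompt: "If above 100.5 degrees Fahrenheit (38 degrees Celsius), subject should inform their study doctor to assess the need for further evaluation". The SAP names no analysis of this log.

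**The concern.** A prolonged QTcF and a fever are events in individual subjects. They are best seen by counting subjects beyond a threshold and listing them, as the SAP already does for laboratory values (SAP 9.3: PCS counts, listings, shift tables and liver-enzyme thresholds). For QTcF no such count is planned, although the protocol supplies the threshold. For temperature the count is promised but has no criterion to run on.

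At stake is whether the safety report can show directly how many subjects per arm crossed the protocol's 500 msec limit or had a raised temperature. This is a dose-exploratory trial that sets up safety reviews to find unanticipated signals with novel agents.

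**Working it through.** The plan states no figure on this point, so there is none to reproduce. The check sets the texts side by side and then illustrates what by-visit means can show.

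**Step 1: vital signs in SAP 9.4 against rows in Table C-2.**

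| Variable in SAP 9.4 | Row in Table C-2 |
|---|---|
| Systolic pressure | yes |
| Diastolic pressure | yes |
| Pulse | yes |
| Weight | yes |
| Body temperature | none |

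Temperature is the only listed variable without a criterion. Appendix C does contain fever grades: row C2 of Table C-1 starts at 37.7 °C, moves to Grade 2 at 38.6 °C and to Grades 3 and 4 at 40 °C. But Appendix C assigns Table C-1 to laboratory findings, and row C2 also uses symptoms, duration and response to medication. Nothing links it to a measured vital sign. What remains for temperature is mean change with a 95% CI and an ANOVA between groups.

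**Step 2: ECG.** The protocol limit is 500 msec. SAP 9.6 specifies no threshold, maximum on-treatment value, change from the pre-dose ECG or listing. SAP 9.1 provides change-from-baseline statistics for laboratory parameters and vital signs, not for ECG. The handling of unscheduled or confirmatory ECGs is not stated.

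**Step 3: what an arm mean shows.** Arm sizes of 20, 40 and 60 come from the randomisation scheme. The documents give no SD for QTcF change, so I assume 15 to 20 msec, and one subject with a rise of 90 msec (range 60 to 120). Shift = rise/n; SE = SD/√n; ratio = shift/SE.

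| n | Shift for 90 msec (60 to 120) | SE at SD 15 / 20 | 90 msec shift in SE units | One subject as % of arm |
|---|---|---|---|---|
| 20 | 4.5 (3.0 to 6.0) | 3.35 / 4.47 | 1.34 / 1.01 | 5.0% |
| 40 | 2.25 (1.5 to 3.0) | 2.37 / 3.16 | 0.95 / 0.71 | 2.5% |
| 60 | 1.5 (1.0 to 2.0) | 1.94 / 2.58 | 0.77 / 0.58 | 1.7% |

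Across the full assumed range the ratio runs from 60/(20 × √60) = 0.39 to 120/(15 × √20) = 1.79. For temperature, one subject 2 °C above baseline moves the mean by 2/20 = 0.10, 2/40 = 0.05 or 2/60 = 0.03 °C.

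**Step 4: units.** (100.5 − 32) × 5/9 = 38.06 °C, so the protocol's two temperature figures agree after rounding.

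**The case against.** The strongest reply is that adverse event reporting already covers the harm. Under Protocol 6.1 any unfavourable sign can be an adverse event. All treatment-emergent events are tabulated (SAP 9.2.3), those leading to discontinuation are tabulated and listed (SAP 9.2.5, 9.2.11), and disposition counts reasons for stopping (SAP 5.0). Serious and opportunistic infections, the target of temperature monitoring, are events of special interest with their own listing and treatment differences. The DMC sees unblinded safety data. This stands: a reader might infer that QT or fever signals would be absent from the safety tables altogether, and the documents do not support that. The route does depend on someone recording an adverse event. Protocol 6.2 does not require one when either figure is crossed, and neither QT prolongation nor fever is itself an event of special interest.

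Three further inferences also fail:

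- *That ECG data are lost.* SAP 9.6 does not exclude unscheduled ECGs; it is silent on them. Protocol 5.6 continues scheduled visits after study drug is stopped unless consent is withdrawn.
- *That ABBV-599 is specially affected.* Nothing in the documents points to a particular QT or fever risk with the combination.
- *That a protocol commitment is broken.* Protocol 7.4 promises outlier percentages only for selected laboratory and vital sign parameters and does not mention ECG.

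It is also fair to say that SAP 9.6 does not mention means, and that SAP 9.1 allows categorical data to be shown as frequencies. The section is underspecified rather than restrictive, but it still names no category to count. Finally, 38 °C belongs to the home log, where it prompts contact with the study doctor; it is not a limit on the clinic reading.

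**Conclusion.** The point holds as a gap in the SAP. The protocol's QTcF stopping limit has no matching subject-level table, and the PCS evaluation promised for body temperature cannot be run because Table C-2 has no row for it. Measured values beyond these figures can therefore be missing from the planned summaries when no adverse event is recorded.

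The text comparison rests on no assumption. The dilution figures are illustrative and depend on the assumed SD and size of rise. In particular, it cannot be said that one outlier always stays within one standard error: at n = 20 the 90 msec example exceeds it at both assumed SDs. The importance is modest. Efficacy inference is unaffected, and the case for change is that a more informative analysis is available from data already collected.

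**What to change.** All changes are SAP wording; clinical management stays as it is.

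- **SAP 9.6:** add, by arm, the number and percentage of subjects whose maximum QTcF after first dose exceeds the protocol's 500 msec. Use scheduled and unscheduled ECGs up to 30 days after last dose. Add a listing of these subjects, and change from the last pre-dose ECG. Lower cut-offs and categories of increase are optional analysis choices; the documents do not supply them.
- **Table C-2:** add a body temperature row, counted as subjects with at least one treatment-emergent value as SAP 9.4 defines it. Above 38 °C is one possible analysis criterion, with a note that the protocol uses this value for the home log.
- **Home log:** state whether it is analysed. If the readings are in the database, report by arm the subjects with at least one reading above 38 °C.

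The cost is one ECG table with its listing, one row in an existing table, and a home-log count if the data are held. The drawback is that a few isolated, unconfirmed outliers will be listed and will need comment.

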## 10.0 Other Analyses

No other analyses are planned.

## 11.0 Interim Analyses

An unblinded interim analysis to review safety will be conducted by an independent internal DMC at 3 time points and ad hoc as needed: when approximately 50% of subjects have completed Week 4 evaluation, when approximately 80% of subjects have completed Week 4 evaluation, and when approximately 80% of subjects have completed Week 12 evaluation. The sponsor, study sites and subjects will remain blinded for the duration of the study.

## 11.1 Data Monitoring Committee

An internal data monitoring committee (DMC) composed of persons independent of study team and with relevant expertise in their field will review unblinded safety data from the ongoing study. The primary responsibility of the DMC will be to protect the safety of the subjects participating in this study.

A separate DMC charter describes the roles and responsibilities of the DMC members, frequency of data reviews, relevant data to be assessed, and general operations.

Since there are no efficacy analyses for early stopping, no alpha adjustment is needed.

## 12.0 Overall Type-I Error Control

Hypothesis testing in the primary analyses (see Section 8.3.3) will be performed in a ranked fashion as follows based on two-sided significance level of  $\alpha = 0.1$ .

- 1) The superiority of ABBV-599 compared to placebo at Week 12 using MMRM.
- The dose-response among ABBV-105 dose groups and the placebo group at Week 12 using MCP-Mod method.

All other tests will be performed at two-sided statistical significance level of  $\alpha = 0.1$  without multiple testing  $\alpha$  adjustment.

Since there are no efficacy analyses for early stopping planned for the DMC review, no alpha spending is needed due to the DMC review.

## 13.0 Version History

### Table 3.SAP Version History Summary

Version	Date	Summary		
1.0	29 May 2018	Original version		
2.0	16 Jul 2018	
 
The changes made between the second and the first version are:
 
Small editorial changes for readability and to maintain consistency with the protocol
 
Clarification of cutoff days for laboratory and vital sign values.
 
An update to the DMC evaluation checkpoints.
 
The addition of the OMERACT Criteria, which was referenced in the safety section, to the Appendix
 
		
3.0	13 June 2019	
 
The changes made between this and the previous version are:
 
An update to visits with ECG data collected in Section 9.6 to maintain consistency with the protocol
 
Addition of an interim efficacy analysis to maintain consistency with the protocol
 
Updated the AESI table to maintain consistency with the protocol
 
Updates to the historical borrowing methods detailed in Appendix D
 
Change of formatting to adhere to a new SAP template
 
		
4.0	23 Jan 2020	
 
The change made between this and the previous version are:
 
Updated Potential Clinically Important Criteria for safety endpoints in Appendix C
 
Removed interim analysis due to protocol amendment
 
Changed secondary endpoints from "Proportion of subjects achieving CR (DAS28 CRP) at Week 12" and "Proportion of subjects achieving LDA (DAS28 CRP) at Week 12" to "Proportion of subjects achieving CR (DAS28 CRP) at all visits" and "Proportion of subjects achieving LDA (DAS28 CRP) at all visits," respectively, as the summaries by visits are of interest.
 
Added "Proportion of subjects achieving LDA (DAS28 CRP) but not CR at all visits" as secondary endpoints, as these summaries are of interest.
 
Added AO analyses for DAS28 CRP and ACR20/50/70 response rates at all visits as sensitivity analyses per protocol.
 
Updated the criteria for Liver-Related Elevations to align with Immunology RA project conventions.
 
		

#### Appendix A. Protocol Deviations

The number and percentage of subjects who reported at least one of the following protocol deviation categories will be provided.

- Subject entered into the study even though s/he did not satisfy entry criteria.
- Subject developed withdrawal criteria during the study and was not withdrawn.
- Subject received wrong treatment or incorrect dose of study.
- Subject took prohibited concomitant medication.

## Appendix B. Definition of Adverse Events of Special Interest

Adverse Events of Special Interest (AESI) will be identified using the following search criteria:

AESI	Type of MedDRA Query	Broad or Narrow Search	SMQ/CMQ Search Criteria
Serious Infections	CMQ		"Infections" – Subset for SAEs
Opportunistic Infection	CMQ		"Opportunistic Infection"
Possible Malignancy	SMQ	Narrow	"Malignancies"
Malignancy	SMQ		"Malignant tumours"
Non-Melanoma Skin Cancer (NMSC)	SMQ	Broad	Skin Malignant tumours (Broad SMQ) removing Melanoma CMQ
Malignancy excluding NMSC			"Malignant tumours" SMQ removing NMSC output
Lymphoma	SMQ		"Malignant Lymphomas"
Hepatic Disorder (Hepatic Events and Increased Hepatic Transaminases)	SMQ	Narrow	"Drug Related Hepatic Disorders"
Gastrointestinal Perforations	SMQ	Narrow	"Gastrointestinal Perforation"
Anemia	CMQ		"Non-Hemolytic and Non-Aplastic Anemias"
Neutropenia	CMQ		"Hematological Toxicity – Neutropenia"
Lymphopenia	CMQ		"Hematological Toxicity – Lymphopenia (Veliparib Product Specific)"
Herpes Zoster	CMQ		"Herpes Zoster"
Creatine Phosphokinase (CPK) Elevation	PT		Search only for the PT of "Blood creatine phosphokinase increased"
Renal Dysfunction	SMQ	Narrow	"Acute Renal, Failure"
Tuberculosis	CMQ		"Tuberculosis"
Adjudicated Cardiovascular Events	Output from CAC		

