3.4 Safety Assessments

Routine safety evaluations include AE monitoring, physical examinations, vital sign measurements, electrocardiogram (ECG), and clinical laboratory testing (hematology, chemistry, and urinalysis) as a measure of safety and tolerability for the entire study duration.

SAEs will be assessed at any dose that results in a death, inpatient hospitalization or prolongation of existing hospitalization, persistent or significant disability/incapacity or a congenital anomaly.

Safety data will be assessed over the course of the study. An independent internal DMC will be created, and unblinded safety assessments will be conducted (Section 7.5). This is to assess unanticipated safety signals with regard to novel agents ABBV-105 and ABBV-599.

An independent Cardiovascular Adjudication Committee (CAC) will adjudicate blinded cardiac and cerebrovascular events. A CAC charter will be prepared separately from the protocol that will define objective, scope, frequency, and triggers of data reviews.

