Table 3. AEs Requiring Supplemental Reports

Adverse Event	Supplemental Report
Cardiac events Myocardial infarction or unstable angina Heart failure Cerebral vascular accident and transient ischemic attack Cardiovascular procedures (SAE Supplemental Procedure eCRF)	MACE eCRF
Discontinuation or interruption of study drug due to a hepatic-related AE A hepatic-related SAE ALT/AST > 8 × ULN or ALT/AST > 3 × ULN with a total bilirubin > 2 × ULN	Hepatic AE eCRF
Renal impairment Renal dysfunction Renal failure Serum creatinine > 2.0 mg/dL	Renal eCRF
Herpes zoster infection	Herpes zoster eCRF
Thrombotic events Non-cardiac, non-central nervous system (CNS) embolic or thrombotic event (i.e., deep vein thrombosis or pulmonary embolism)	Embolic and Thrombotic (non-cardiac, non-CNS) eCRF

If an AE meets any of the following criteria, it is to be reported to AbbVie as an SAE within 24 hours of the site being made aware of the SAE:

Death of Subject	An event that results in the death of a subject.
Life-Threatening	An event that, in the opinion of the investigator, would have resulted in immediate fatality if medical intervention had not been taken. This does not include an event that would have been fatal if it had occurred in a more severe form.
Hospitalization or Prolongation of Hospitalization	An event that results in an admission to the hospital for any length of time or prolongs the subject's hospital stay. This does not include an emergency room visit or admission to an outpatient facility.
Congenital Anomaly	An anomaly detected at or after birth, or any anomaly that results in fetal loss.
Persistent or Significant Disability/Incapacity	An event that results in a condition that substantially interferes with the activities of daily living of a study subject. Disability is not intended to include experiences of relatively minor medical significance such as headache, nausea, vomiting, diarrhea, influenza, and accidental trauma (e.g., sprained ankle).

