Important Medical Event Requiring Medical or Surgical Intervention to Prevent Serious Outcome An important medical event that may not be immediately lifethreatening or result in death or hospitalization, but based on medical judgment may jeopardize the subject and may require medical or surgical intervention to prevent any of the outcomes listed above (i.e., death of subject, life threatening, hospitalization, prolongation of hospitalization, congenital anomaly, or persistent or significant disability/incapacity). Additionally, any elective or spontaneous abortion or stillbirth is considered an important medical event. Examples of such events include allergic bronchospasm requiring intensive treatment in an emergency room or at home, blood dyscrasias or convulsions that do not result in inpatient hospitalization, or the development of drug dependency or drug abuse.

All AEs reported from the time of study drug administration until 30 days after discontinuation of study drug administration will be collected, whether solicited or spontaneously reported by the subject. In addition, SAEs and protocol-related nonserious AEs will be collected from the time the subject signs the study-specific informed consent.

AbbVie will be responsible for Suspected Unexpected Serious Adverse Reactions (SUSAR) reporting for the Investigational Medicinal Product (IMP) in accordance with global and local requirements.

AEs will be monitored throughout the study to identify any of special interest that may indicate a trend or risk to subjects.

Adverse Events of Special Interest

The following adverse events of special interest (AESI) will be monitored during the study:

- Serious infections
- Opportunistic infections
- Herpes zoster
- Tuberculosis
- Malignancy (all types)
- Gastrointestinal perforations
- Adjudicated cardiovascular events (e.g., major adverse cardiovascular event [MACE])
- Anemia
- Neutropenia
- Lymphopenia
- Increased serum creatinine and renal dysfunction
- Hepatic events and increased hepatic transaminases
- Elevated creatine phosphokinase (CPK)

• Embolic and thrombotic events (non-cardiac, non-CNS).

Adverse Event Severity and Relationship to Study Drug

The investigator will classify AEs according to the Rheumatology Common Toxicity Criteria v.2.0 (Appendix F).

If no grading criteria are provided for the reported event, then the event should be as follows:

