## 3.4 Safety Endpoints

Safety evaluations include adverse event (AE) monitoring, physical examinations, vital sign measurements, electrocardiograms (ECGs), and clinical laboratory testing (hematology, chemistry, and urinalysis) as a measure of safety and tolerability for the entire study duration.

Serious AEs (SAEs) will be assessed at any dose that results in a death, inpatient hospitalization or prolongation of existing hospitalization, persistent or significant disability/incapacity or a congenital anomaly.

Safety data will be assessed over the course of the study. An independent internal Data Monitoring Committee (DMC) will be created and unblinded safety assessments will be conducted. This is to assess unanticipated safety signals with regards to novel agents ABBV-105 and ABBV-599. The study team, study sites and subjects will remain blinded for the duration of the study.

An independent external Cardiovascular Adjudication Committee (CAC) will adjudicate blinded cardiac, cerebrovascular and thromboembolic events. A CAC charter will be

prepared separately from the protocol that will define objective, scope, frequency, and triggers of data reviews.

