#### 8.4 Secondary Efficacy Analyses

Continuous efficacy variables will be analyzed using MMRM method. It will be used for primary inference purpose the same way as for primary efficacy endpoint analysis.

Categorical efficacy variables will be analyzed using the CMH test controlling for stratification variables. The risk difference and 90% confidence intervals for the differences in each comparison will be constructed. NRI imputation will be used for missing data imputation. Point estimate of the response rate for each treatment group will also be summarized with a two-sided 90% confidence interval using Wilson's score method.

In addition, as observed (AO) analyses will be used as sensitivity analyses for DAS28 (CRP) and ACR20/50/70 response rates at all visits.

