### 9.2.2 Adverse Event Overview

An overview of AEs will be presented consisting of the number and percentage of subjects experiencing at least one event for each of the following AE categories:

- All TEAEs
- Treatment-emergent serious adverse events (SAEs)
- Treatment-emergent severe adverse events
- TEAEs reasonably possibly related to study drug
- TEAEs of special interest (AESIs)
- TEAEs leading to discontinuation of study drug
- TEAE leading to death
- All deaths

Additional AEs may be considered for tabulation/summary based on recommendations from Clinical and Safety as deemed appropriate.

For AESIs, the point estimate and 95% CI (using normal approximation) will be provided for the treatment difference in AE percentages.

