## 9.2.6 Adverse Events of Special Interest

The Adverse Events of Special Interest (AESI) categories will be summarized and presented by "as treated" treatment group and overall using SOC and MedDRA PT. The AESI categories will be identified by the following search criteria per Standard MedDRA Queries (SMQs)/Company MedDRA Queries (CMQs) in Appendix B.

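### SAP Appendix B omits the protocol's embolic/thrombotic AESI, the two documents give the CAC different scopes, and the normal-approximation CI for AESI differences is unreliable at low rates

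*SAP*

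**What the plan says.** Protocol 6.1 lists 14 AESIs. The last, "Embolic and thrombotic events (non-cardiac, non-CNS", is an entry of its own, separate from adjudicated cardiovascular events. Protocol Table 3 gives it a dedicated supplemental eCRF, describing a non-cardiac, non-CNS "embolic or thrombotic event (i.e., deep vein thrombosis or pulmonary embolism".

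SAP 9.2.6 states: "The AESI categories will be identified by the following search criteria per Standard MedDRA Queries", and points to Appendix B, which opens "Adverse Events of Special Interest (AESI) will be identified using the following search criteria". That table has 17 rows. None is embolic, thrombotic, DVT or PE. The only vascular row is adjudicated cardiovascular events, whose source is the CAC output. The SAP version history records that version 3.0 updated the AESI table to agree with the protocol.

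On adjudication, Protocol 3.4 says: "An independent Cardiovascular Adjudication Committee (CAC) will adjudicate blinded cardiac and cerebrovascular events". SAP 3.4 says the committee "will adjudicate blinded cardiac, cerebrovascular and thromboembolic events". Both leave scope to a separate charter.

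On intervals, SAP 9.2.2 says: "For AESIs, the point estimate and 95% CI (using normal approximation) will be provided for the treatment difference in AE percentages". The planned arms (SAP 2.3) are 60 for ABBV-599, 40 in each of four arms, and 20 for placebo.

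**The concern.** A programmer who follows Appendix B would produce no embolic/thrombotic AESI summary, although the protocol defines that category and collects data for it on its own form. Whether the CAC row picks these events up depends on which document's CAC scope is followed. Even under the SAP's wider scope they would be merged with cardiovascular events that the protocol lists separately. A search definition chosen after unblinding would be post hoc for a safety category, and safety is part of the main objective.

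The interval is a separate matter. The unpooled normal-approximation (Wald) interval estimates its variance from the observed proportions. An arm with no events contributes zero variance, however small the arm. With rare events and 20 placebo subjects, that can give a zero-width interval or make a small imbalance appear to exclude zero.

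**Working it through.** **Row-by-row match**

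| Protocol 6.1 AESI | Appendix B |
|---|---|
| Serious infections; opportunistic infections; herpes zoster; tuberculosis | one row each |
| Malignancy | five rows (possible malignancy, malignancy, NMSC, malignancy excluding NMSC, lymphoma) |
| GI perforations; anemia; neutropenia; lymphopenia | one row each |
| Creatinine/renal dysfunction; hepatic events; CPK elevation | one row each |
| Adjudicated cardiovascular events | one row (CAC output) |
| Embolic and thrombotic, non-cardiac, non-CNS | none |

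Twelve AESIs with one row plus malignancy with five makes 17 rows covering 13 AESIs. One of the 14 is absent.

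**Interval: inputs**

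Arm sizes are from SAP 2.3; 240 split 3:2:2:2:2:1 gives 60/40/40/40/40/20. The documents state no AESI rates, so every rate below is an assumption. SAP 9.2.2 does not name the arm pairs, so I take 60 vs 20, 40 vs 20 and 60 vs 40.

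Wald: d ± 1.96·√[p1(1−p1)/n1 + p2(1−p2)/n2], with d = p1 − p2. Newcombe combines the two single-arm Wilson limits (l, u): lower = d − √[(p1−l1)² + (u2−p2)²], upper = d + √[(u1−p1)² + (p2−l2)²].

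*No events, 0/60 vs 0/20.* Wald is [0%, 0%]. The Wilson upper limit for 0/n is z²/(n+z²): 3.84/63.84 = 6.0% and 3.84/23.84 = 16.1%. Newcombe is therefore [-16.1%, +6.0%]; Miettinen-Nurminen is [-16.3%, +6.1%].

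*Four events, 4/60 vs 0/20.* The Wald SE is √(0.0667×0.9333/60) = 0.0322, all from the larger arm. The interval is 6.67% ± 6.31% = [+0.4%, +13.0%] and excludes zero. The Wilson limits for 4/60 are 2.6% and 15.9%. Newcombe's lower limit is 6.67 − √(4.04² + 16.11²) = −9.9%, and its upper limit is +15.9%. Miettinen-Nurminen is [-9.9%, +16.0%]. Fisher's exact p is 0.57.

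*Probability of zero width* is (1−p1)^n1 × (1−p2)^n2. At 1%/1%, 60 vs 20: 0.99^80 = 44.8%. At 2%/1%: 0.98^60 × 0.99^20 = 24.3%. At 1%/1%, 40 vs 20: 0.99^60 = 54.7%.

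*Exact coverage of the nominal 95% interval*, summing over all binomial outcomes, 60 vs 20:

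| Assumed rates | Wald | Newcombe |
|---|---|---|
| 1% / 1% | 99.7% | 99.0% |
| 2% / 1% | 75.1% | 99.4% |
| 2% / 2% | 97.8% | 97.9% |
| 3% / 1% | 86.1% | 99.2% |
| 5% / 2% | 94.8% | 97.4% |
| 5% / 5% | 86.9% | 96.9% |
| 10% / 10% | 88.0% | 96.4% |
| 15% / 15% | 92.1% | 95.9% |
| 20% / 20% | 92.9% | 95.5% |

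For the other pairs, Wald coverage at 2%/1% is 63.4% (40 vs 20) and 79.4% (60 vs 40). At 5%/5% it is 94.8% and 93.8%.

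*False signals at 5%/5%, 60 vs 20.* With 0/20 on placebo, Wald excludes zero once x > 60×3.84/63.84 = 3.6, that is, from 4 events. P(X ≥ 4 of 60) = 0.353 and P(0 of 20) = 0.95^20 = 0.358; their product is 12.6%. The full enumeration also gives 12.6%, against a nominal 2.5%.

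**The case against.** The strongest counter-case has five parts.

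- **The omission is partly handled.** The eCRF captures the events, SOC/PT outputs show them, and SAP 9.2.2 lets further AEs be tabulated on clinical and safety advice. Under the SAP's CAC scope the CAC row could carry them. This is true, and no data are lost. What is missing is the pre-specified separate category.
- **The CAC difference may be wording only.** Protocol 3.4 does not say it covers only those events, and the charter, which is not available here, may settle it. This stands as a caution, but the two texts still differ and neither secures the fallback.
- **The CI may apply only to the any-AESI line.** SAP 9.2.2 has a single AESI line, and SAP 9.2.6, which gives the by-category summaries, mentions no CI. This is a fair reading. Under it, with assumed pooled rates of 15% to 20%, coverage is 92% to 93%, which is mild.
- **The low coverage at 2%/1% largely restates the zero-width problem.** At 60 vs 20, 24.3 of the 24.9 points of non-coverage come from the 0/60 vs 0/20 outcome. This is correct, so the two figures should not be counted as separate evidence. The excess at 5%/5% is a distinct effect, but it comes almost wholly from 0/20 on placebo and is much smaller for the other arm pairs.
- **Score intervals are conservative here and no decision rule depends on them.** At an assumed 10% vs 2%, 60 vs 20, Newcombe's lower limit exceeds zero in only 2.3% of trials. This stands: the change gives a more honest statement of uncertainty and does not improve signal detection.

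**Conclusion.** The concern holds and should be fixed. The missing row and the differing CAC wording are established from the text and need no assumption. Following the SAP as written, the protocol's embolic/thrombotic AESI gets no separate summary.

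The interval point holds with conditions. Read by category, the Wald interval can collapse to zero width (45% of the time at an assumed 1%/1%, 60 vs 20). It can also exclude zero too often against placebo (12.6% at 5%/5%). The error is not one-directional: coverage is above nominal at equal very low rates and close to nominal at, for example, 5%/2%. Read as the pooled line only, the shortfall is two to three percentage points at 15% to 20%. The intervals are descriptive, and no efficacy analysis or stopping rule depends on them.

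**What to change.** 1. Add an Appendix B row for non-cardiac, non-CNS embolic and thrombotic events, naming its source: a MedDRA query or the CAC output.
2. Reconcile the CAC scope in Protocol 3.4 and SAP 3.4, and check both against the charter.
3. In SAP 9.2.2, state whether the CI is for the any-AESI line, each category, or both. Replace the normal approximation with Newcombe or Miettinen-Nurminen. This sits easily beside the "two-sided 90% confidence interval using Wilson's score method" in SAP 8.4, although Wilson is specified there for single-arm response rates only; Newcombe's difference interval is built from it.

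The cost is one table row, one line on CAC scope, one clarifying phrase and a different CI option, all before unblinding. The price of the score interval is width. At 60 vs 20, Newcombe's lower limit exceeds zero in under 0.1% of trials at 5%/5%, and also in under 0.1% at 5%/2%, where Wald's does in 23.5%.
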